6.1.4 Impact of Childhood Neurologic Disability (ICND) Scale

The Impact of Childhood Neurologic Disability (ICND) scale was developed to evaluate the impact that a child's condition has on the child's and the family's everyday life at the present time and during the previous 3 months (Camfield et al. 2003). The parent or other caregiver evaluates the effect of a condition or health problem on 11 aspects of the child's or the family's life as "A lot", "Some", "A little", "Not at all", or "Does not apply". The four conditions or health problems are 1) inattentiveness, impulsivity, or mood, 2) ability to think and remember, 3) neurologic or physical limitations, and 4) epilepsy.

The caregiver then rates overall quality of life of the subject by responding to the following: "Please rate your child's overall 'Quality of Life' on the scale below. Choose the number which you feel is best and circle it". The choices range from 1 ("Poor") to 6 ("Excellent").

The assessment will be administered at Baseline and Visit 5.

6.1.5 Rett Syndrome Clinician Rating of Hand Function (RTT-HF)

The Rett Syndrome Clinician Rating of Hand Function is a clinician completed clinical assessment of the subject's ability to use her hands for functional purposes (such as reaching for and grasping objects, self-feeding or drawing). The assessment is made on an 8-point Likert scale (0-7) with 0 denoting normal functioning and 7 the most severe impairment. This rating is a further development of the RTT-DSC Hand Use Rating used in Study Neu-2566-RETT-002.

The assessment will be administered at Baseline and at all other designated visits.

6.1.6 Rett Syndrome Clinician Rating of Ambulation and Gross Motor Skills (RTT-AMB)

The Rett Syndrome Clinician Rating of Ambulation and Gross Motor Skills is a clinician completed clinical assessment of the subject's ability to sit, stand, and ambulate (e.g., walking, running, climbing stairs). The assessment is made on an 8-point Likert scale (0-7) with 0 denoting normal functioning and 7 the most severe impairment. This rating is a further development of the RTT-DSC Ambulation Rating used in Study Neu-2566-RETT-002.

The assessment will be administered at Baseline and at all other designated visits.

6.1.7 Rett Syndrome Clinician Rating of Ability to Communicate Choices (RTT-COMC)

The Rett Syndrome Clinician Rating of Ability to Communicate Choices is a clinician completed clinical assessment of the subject's ability to communicate her choices or preferences, which can include the use of nonverbal means such as eye contact or gestures. The assessment is made on an 8-point Likert scale (0-7) with 0 denoting normal functioning and 7 the most severe impairment. This rating is a further development of the RTT-DSC Language/Communication Rating used in Study Neu-2566-RETT-002.

The assessment will be administered at Baseline and at all other designated visits when the visit takes place in the clinic. When a study visit takes place off-site, the RTT-COMC should be completed if possible, but it is not required.

6.1.8 Rett Syndrome Clinician Rating of Verbal Communication (RTT-VCOM)

The Rett Syndrome Clinician Rating of Verbal Communication is a clinician completed clinical assessment of the subject's ability to communicate verbally (e.g., words and phrases). The assessment is made on an 8-point Likert scale (0-7) with 0 denoting normal functioning and 7 the most severe impairment. This rating is a further development of the RTT-DSC Language/Communication Rating used in Study Neu-2566-RETT-002.

The assessment will be administered at Baseline and at all other designated visits.

6.1.9 Rett Syndrome Caregiver Burden Inventory (RTT-CBI)

The RTT-CBI is a syndrome-specific, caregiver-completed questionnaire that is based on the Caregiver Burden Inventory designed for Alzheimer's disease ([Lane et al. 2017](#); [Novak and Guest 1989](#)). The scale is intended to directly address caregiver burden and indirectly assess the significance of treatment effects on function in the context of activities of daily living. Caregivers rate how often a given statement describes their feeling or experience. Frequency ratings are on a 5-point Likert scale including: 0-never; 1-rarely; 2-sometimes; 3-frequently and 4-nearly always. As in the original Caregiver Burden Inventory, the RTT-CBI has 24 negatively worded items (items 1 through 24) yielding a total score up to 96. The RTT-CBI also includes 2 positively worded items (items 25 and 26) that comprise the Optimism Index ([Lane et al. 2017](#)). In this study, as in the 2 previous studies of trofinetide in Rett syndrome, the total score is defined as the total Burden score (items 1-24).

The RTT-CBI will be completed at Baseline, Visit 3, and Visit 5.

6.2 Safety Assessments

6.2.1 Physical Examination

A general physical examination will be conducted at Baseline and at all other designated visits. When a study visit takes place off-site, the physical examination will not be required. The physical exam procedures will include the following organ systems:

- Neurological
- Head, ears, eyes, nose, and throat
- Skin
- Cardiovascular
- Respiratory
- Abdomen
- Genitourinary (optional)
- Musculoskeletal

6.2.2 Vital Signs

Vital signs will include body temperature, resting respiration rate, sitting systolic and diastolic blood pressure, and pulse rate. The sitting blood pressure will be measured after the subject has been sitting for ≥ 3 minutes.

Vital signs to be measured at Baseline and at all other designated visits.

6.2.3 Height, Weight, and Body Mass Index

Height will be measured at Baseline and Visit 5.

Weight will be measured at Baseline, Visit 2, Visit 3, Visit 4, and Visit 5 when the visit takes place in the clinic. Measurement of weight is necessary at Baseline in order to determine the starting dose. When a study visit takes place off-site, weight should be measured whenever possible.

Body mass index will be calculated using the following formula:

$$\text{Weight (kg)} / [\text{height (m)}]^2.$$

6.2.4 Electrocardiograms

All 12-lead ECGs will be complete, standardized recordings, whenever possible. ECGs will be completed in triplicate at Visit 1 (Baseline) both before dosing and 2-3 hours after dosing and at Visit 5 (Week 40/EOT). For those subjects who completed the antecedent study, the

ECG taken at the Week 12/EOT visit in the antecedent study is the predose Baseline ECG of the present study. Subjects who were discontinued from the preceding study before completion because of the COVID-19 public health emergency and subjects who completed but were prevented from entering the present study because of the COVID-19 public health emergency, will have ECGs completed in triplicate at the Baseline visit which will be considered the predose Baseline ECG of the present study. A single ECG will be completed at Visit 2 (Week 2), Visit 3 (Week 12), and Visit 4 (Week 26). For visits at which more than one ECG is completed, the average QTcF interval of all legible ECGs will be used to determine the QTcF interval for that visit.

The subject should rest for ≥ 5 minutes in a supine position before before the ECG is obtained. If it is impractical to rest in supine position due to the subject's medical condition, the subject may remain in a partial supine or other position (e.g., upright in wheelchair) for ≥ 5 minutes before the ECG is obtained and when the ECG is obtained. ECG tracings (paper or electronic) will be reviewed and interpreted by a qualified clinician for prolongation of the QTcF interval and for other cardiac irregularities. ECG tracings and results (ventricular rate, PR, QRS, QT, QTcF and QTcB intervals) will be included in the subject's study records.

At Baseline, the average QTcF interval of all legible ECGs will be used to determine eligibility. ECGs will also be read by a qualified central reader. The central reading will be the reading that is entered in the database. The results from the reports from the central reader will also be reviewed by the Investigator.

6.2.4.1 Post-Enrollment QTcF Interval Stopping Criteria

In the event that a post-enrollment QTcF duration of ≥ 500 ms or an increase of ≥ 60 ms compared to the average QTcF interval at Baseline of the present study (before dosing) is observed, study drug administration is to be discontinued. For visits at which more than one ECG is completed, the average QTcF interval of all legible ECGs will be used to determine the QTcF interval for that visit.

6.2.5 Laboratory Evaluations

Laboratory evaluations will be completed according to the schedule presented in [Table S-2](#) and procedures detailed in the laboratory manual. Additional safety testing may be performed at the discretion of the Investigator or designee.

Clinical laboratory sample collection is not required to be completed under fasting conditions. The laboratory evaluations will include the following:

- Clinical chemistry serum tests

- Sodium (Na), potassium (K), chloride (Cl), phosphorus (P), calcium (Ca), carbon dioxide (CO₂), blood urea nitrogen (BUN), creatinine (CR), uric acid
- Alanine aminotransferase (ALT), aspartate aminotransferase (AST), gamma-glutamyl transpeptidase (GGT), alkaline phosphatase (ALP), total bilirubin (TBIL), lactate dehydrogenase (LDH)
- Glucose
- Albumin (ALB), total protein
- Thyroid stimulating hormone (TSH), free T3, and free T4
 - Thyroid function tests will be performed at Visit 1 (Baseline) and Visit 5
- Pregnancy test
 - A serum pregnancy test will be performed at all designated visits ([Table S-2](#)) for subjects of childbearing potential
- Hematology tests
 - Complete blood count (CBC) including:
 - White blood cell (WBC) count
 - Complete differential (relative and absolute)
 - Hematocrit (Hct), hemoglobin, red blood cells (RBC), platelets
 - Reticulocyte count
- Urinalysis
 - Blood, RBCs, WBCs, protein, glucose, ketones, specific gravity, pH
 - Reasonable efforts will be made to collect a urine sample from all subjects. When collection of a urine sample proves impractical or impossible (e.g., because the subject is incontinent or unable to cooperate), failure to collect a urine sample will be recorded in the subject's eCRF, and will not be considered a protocol deviation

Subjects for whom the Baseline visit of this study is not on the same day as the Week 12/EOT visit of the antecedent study (e.g., subjects in the antecedent study who were prevented from entering this study by the COVID-19 public health emergency) will have blood drawn for Baseline values three to fourteen days before the Baseline visit. The investigator should have the results of the following standard laboratory studies available for review before enrolling the subject: the basic metabolic panel (Na, K, Cl, P, Ca, CO₂, BUN, and CR), serum glucose,

the liver function tests (ALT, AST, GGT, ALP, TBIL and LDH), serum pregnancy test (if the subject is of childbearing potential), and CBC.

6.3 Caregiver Diary

A semi-structured caregiver diary will be completed during treatment in which caregivers will record seizures and seizure-like spells if they are present.

At the Baseline visit, the clinician will review subject's seizure profile (if applicable) and will help to characterize the subject's typical seizure types. These are recorded in the caregiver diary.

For the 2 days before scheduled visits as well as the morning of the scheduled visit, the dates and times of trofinetide dosing, concomitant medication dosing, and meals will be recorded in the caregiver diary. Daily study drug dosing, including any dose modifications, missed or partial doses, will also be recorded in the caregiver diary.

The caregiver diary will be completed and collected on an ongoing basis throughout the study from Baseline to Visit 5. The clinician will verbally ask about AEs (see [Section 7.3.1](#)), review the events recorded in the diary with the caregiver and will make a clinical evaluation, including an evaluation of whether an AE will be reported.

6.4 Pharmacokinetic Assessments

Pharmacokinetic blood samples will be collected for measurement of whole blood concentrations of trofinetide and any relevant possible metabolites identified.

Pharmacokinetic blood samples will be collected for trofinetide concentration measurements at the Baseline visit (both before dosing and after dosing) and at Visit 2, Visit 3, Visit 4, and Visit 5 in accordance with the sampling schedule outlined below ([Table 6-1](#)).

The PK sample taken at the Week 12/EOT visit in the antecedent study is the predose PK blood sample for the present study. The second PK sample to be taken at the Baseline visit (Visit 1), approximately 2-3 hours after dosing, will take place as soon as possible after the postdose ECG is performed.

PK samples at Visits 2, 3, 4, and 5 will be collected at one of the following time intervals:

- 2-3 hours after dosing
- 4-6 hours after dosing
- 7-11 hours after dosing

Every effort should be made to collect PK samples at discrete time intervals during Visits 2, 3, 4, and 5. However, if the interval is the same at each visit, then the collection time should

vary within that interval. The following scenario is only for illustrative purposes, a number of other scenarios are possible.

- For example, if the time interval of 4-6 hours after dosing is used for Visit 2, 3, 4, and 5, then every effort should be made to collect PK samples at 4, 4.5, 5, and 6 hours after dosing, respectively.

Pharmacokinetic samples will also be collected, if possible, at any ET visit or the visit immediately following any SAE or following any AE leading to discontinuation, even if it is an unscheduled visit.

For all scheduled PK samples (and for unscheduled samples if possible), the dates and times of administration of the study drug, the dates, times and content of the meals, and the dates and times of the administration of concomitant medication over the 2 days prior to and on the morning of the PK sample draw, as well as the date and time of the sample draw, will be recorded. For samples collected from subjects who experience any SAE or experience an AE leading to discontinuation, the date and time of the last dose of study drug prior to the SAE or AE leading to discontinuation will also be recorded.

Table 6-1 PK Sampling Times

Visit	Timing of Sample (relative to start of dosing on the visit day)	Week of Treatment
1 (Baseline)	Any time before dosing and 2 – 3 hours after dosing (after ECG)	Week 0 (Baseline)
	2 – 3 hours after dosing or 4 – 6 hours after dosing	Weeks 2, 12, 26, and 40/EOT
2, 3, 4, and 5	7 – 11 hours after dosing	

Abbreviations: ECG=electrocardiogram; EOT=end of treatment

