The confidential information in this document is provided to you as a Principal Investigator or Consultant for review by you, your staff, and the applicable institutional review board/ethics committee. Your acceptance of this document constitutes agreement that you will not disclose the information contained herein to others without written authorization from the Sponsor.

Principal Investigator

Signature

Date

Name (printed)

PROTOCOL SYNOPSIS¹

Protocol Number	ACP-2566-004	
EudraCT Number	Not applicable	
Protocol Title	A 40-Week, Open-label Extension Study of Trofinetide for the Treatment of Girls and Women with Rett Syndrome	
Name of Investigational Product	Trofinetide oral solution	
Indication	Rett syndrome	
Phase of Development	3	
Sponsor	ACADIA Pharmaceuticals Inc. 	
Primary Objective	
 To investigate the safety and tolerability of long-term treatment with oral trofinetide in girls and women with Rett syndrome 	Primary Endpoints
		
 Treatment-emergent adverse events (TEAEs) Serious adverse events (SAEs) Withdrawals due to adverse events (AEs) Potentially clinically important changes in other safety assessments
Secondary Objectives	
 To investigate the efficacy of long-term treatment with oral trofinetide in girls and women with Rett syndrome 	Secondary Endpoints
		
 Rett Syndrome Behaviour Questionnaire (RSBQ) total score – Change from Baseline to Week 40 Clinical Global Impression–Improvement (CGI-I) Score at Week 40 (assessing

¹ NOTE: In this protocol, as in FDA guidance documents, the use of the word "should" means that something is suggested or recommended, but not required. If something "may be" done, the meaning is that something is allowed, but not required. The terms "must" and "will" mean that something is required.

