5.1.3 Dosing and Administration

5.1.3.1 Dosing

The dose assigned to each subject in the antecedent double-blind study, ACP-2566-003, was based on the subject's weight at Baseline of that study. In this study, the dose assigned to each

subject is based on the subject’s weight at Baseline of this study. The assigned dose is based on the range of weight in which the subject falls at Baseline (Table 5–1), unless the subject’s dose was set lower in the antecedent study for reasons of tolerability. In that case the subject’s assigned dose for this study will be the final dose from the antecedent study.

The dose will not be increased or decreased if the subject’s weight at a postbaseline visit puts them in a new weight category. The dose may be decreased during the study for poor tolerability as discussed in [Section 5.1.3.2](#). Study drug is administered twice a day, once in the morning and once in the afternoon or evening. There should be at least 8 hours between doses.

Table 5–1 Dosing Schedule Based on Weight at Baseline of the Present Study

Weight	Dose	Total Daily Dose
12-20 kg	30 mL (6 g) BID	60 mL (12 g)
>20-35 kg	40 mL (8 g) BID	80 mL (16 g)
>35-50 kg	50 mL (10 g) BID	100 mL (20 g)
>50 kg	60 mL (12 g) BID	120 mL (24 g)

Abbreviation: BID=twice daily

The first dose of study drug for the present study is intended to be administered after all Baseline assessments are completed. Since in most cases, the subject will have taken the last dose of study drug from the antecedent study on the morning of the Baseline visit for this study, the first dose of study drug for this study will then be administered either as an evening dose after the Baseline visit has been completed or on the following day. An ECG must be performed 2-3 hours after the first dose and a PK sample will be taken upon completion of the ECG. Off-site dosing at Baseline may only be done if it is possible to record an ECG 2-3 hours after the first dose and draw blood for a PK sample upon completion of the ECG. The Investigator must review the ECG readings with special attention to the QTcF interval before the subject can receive another dose of study drug. Off-site dosing at Baseline must first be approved by the Sponsor or Medical Monitor.

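### A 7–11 h PK sample can follow the visit-day second dose, but the protocol requires dose clock times only up to that morning

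*Protocol*

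**What the plan says.** **Sampling.** Protocol section 6.4 allows samples at Visits 2–5 in one of three intervals, the last being "7-11 hours after dosing". The timing column of Table 6-1 is headed "Timing of Sample (relative to start of dosing on the visit day", which reads most naturally as the first dose that day.

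**Dosing.** Section 5.1.3.1 states: "Study drug is administered twice a day, once in the morning and once in the afternoon or evening". It adds: "There should be at least 8 hours between doses". The synopsis footnote defines the word should: it "means that something is suggested or recommended, but not required".

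**Recording.** Section 6.3 reads: "For the 2 days before scheduled visits as well as the morning of the scheduled visit, the dates and times of trofinetide dosing", with meals and concomitant medication in the same list. Section 3.1.1 repeats this rule. Section 6.4 and the synopsis cover study drug, meals and concomitant medication "over the 2 days prior to and on the morning of the PK sample draw", and also require the date and time of the draw. Separately, the diary records daily dosing, including modified, missed or partial doses, with no clock time mentioned. The time of a last dose is expressly required only for samples tied to an SAE or to an AE leading to discontinuation, and there it means the last dose before the event.

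**Use.** Protocol section 9.5.4 plans population PK if data allow, under a separate data analysis plan. SAP section 15 summarises concentrations by visit and leaves the modelling to a separate report.

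**The concern.** The recording window closes in the morning, but the sampling interval runs to 11 h after the first dose and the second dose may come before then. No text says that the draw precedes the second dose, or that the time of a visit-day afternoon or evening dose is recorded. A site following the protocol exactly can therefore deliver a sample whose time since the most recent dose is unknown.

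For example, take doses at 08:00 and 16:00 and a draw at 18:00. The required record shows a morning dose and a draw 10 h later. The sample is in fact 2 h after a dose, close to peak.

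The 7–11 h samples are the latest scheduled at Visits 2–5, so they carry much of the information on decline and trough. Near-peak values read as late values would make elimination look slower than it is. The error would pass into the exposure measures for the PK/PD objective.

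**Working it through.** The plan states no figure to reproduce. The check is clock arithmetic, followed by a model to size the consequence.

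**Inputs**
- Sampling interval 7–11 h (protocol section 6.4, Table 6-1).
- Recommended minimum gap 8 h (section 5.1.3.1).
- Half-life 5.3–6.1 h, the range of geometric means across three dose groups (section 1.3).
- Absorption rate ka: not in the documents; assumed 0.5, 1 and 2 per hour.

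**1. Clock times.** Time since second dose = time since first dose − gap. With a gap of 8 h:
- 9 h is 1 h post-dose.
- 10 h is 2 h post-dose.
- 11 h is 3 h post-dose.

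Of the 4 h interval (11 − 7), 3 h (11 − 8) lie after such a dose. Any gap under 11 h leaves some overlap: with a 10 h gap, an 11 h draw is 1 h post-dose. With a 12 h gap there is none.

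**2. Size of an 8 h timing error.** The decay factor is 2^(8/half-life):
- 2^(8/5.3) = 2.85
- 2^(8/6.1) = 2.48

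**3. Concentration against that expected with no second dose.** One-compartment oral model at steady state, equal doses at 0 h and 8 h each day, k = ln 2 / half-life. Each dose contributes ka/(ka − k) × (e^(−k·t) − e^(−ka·t)). The ratio is the summed concentration with the visit-day second dose, divided by the sum without it.

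| Half-life (h) | ka (per h) | Ratio at 10 h | Ratio at 11 h |
|---|---|---|---|
| 5.3 | 0.5 | 2.29 | 2.65 |
| 5.3 | 1 | 3.00 | 3.25 |
| 5.3 | 2 | 3.37 | 3.42 |
| 5.7 | 0.5 | 2.18 | 2.51 |
| 5.7 | 1 | 2.81 | 3.03 |
| 5.7 | 2 | 3.14 | 3.18 |
| 6.1 | 0.5 | 2.09 | 2.39 |
| 6.1 | 1 | 2.66 | 2.86 |
| 6.1 | 2 | 2.95 | 2.99 |

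The range is about 2.1 to 3.4.

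**4. Against the 2 h level.** This uses a simpler bolus approximation, with earlier doses 12 h apart and half-life 5.7 h:
- Accumulation R = 1/(1 − 2^(−12/5.7)) = 1.30.
- Expected 10 h level relative to 2 h: 2^(−8/5.7) = 0.378, a fall of 62%.
- Ratio from the second dose: 1 + 2^(8/5.7)/R = 1 + 2.645/1.303 = 3.03.
- Level with the second dose: 0.378 × 3.03 = 1.15 times the 2 h level.

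An expected fall of 62% becomes an apparent rise of about 15%.

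**The case against.** **The time may be captured elsewhere.** The eCRF and the population PK data analysis plan are not in the documents. A reader might infer that these samples will be analysed as 10 h values, or that the second-dose time is never collected. The documents support neither: the SAP summarises by visit only, and the unseen documents may capture or impute the time. This stands, and it makes the bias conditional. Imputation is not a safe repair, however: assuming a 12 h gap would place the dose after a 10 h draw.

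**Section 6.4 can be read more widely.** Its time limit could grammatically attach to concomitant medication alone, leaving study-drug times unrestricted. Sections 3.1.1 and 6.3 close that route for the diary, because they place trofinetide dose times inside the morning limit.

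**Eight hours is an unusual gap.** The synopsis and section 3.1.1 describe morning and evening dosing, and section 5.1.3.2 does so for the final dose; only section 5.1.3.1 mentions the afternoon. This stands as to frequency. Nor should 8 h be called the earliest permitted time, since it is a recommendation. The 3 h in 4 overlap is interval width under an 8 h gap, not a share of samples.

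**Other samples inform elimination.** The 4–6 h samples also contribute, so the late ones are the latest information, not the only information.

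**Visit 1 adds little.** An evening first dose falls outside the morning limit, but the ECG is due 2–3 h after that dose and the PK sample follows on its completion, so procedure largely fixes the time.

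**The main results are untouched.** PK is not the primary objective. The safety and efficacy summaries do not depend on these times.

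**Conclusion.** The recording rule is too narrow for the sampling interval it serves. Followed exactly, it can leave a late PK sample without a known time since the most recent dose. With a second dose at 8 h and a draw at 10–11 h, the concentration would be about 2.1 to 3.4 times the value expected without that dose. This rests on one-compartment kinetics, the half-lives in section 1.3 and assumed absorption rates.

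Bias in half-life and trough (upward) and clearance (downward) follows only if four things coincide: the last interval is used, a second dose precedes the draw, its clock time is not captured elsewhere, and the sample is treated as late. The documents give no frequency for this, and morning and evening dosing probably keeps it low. The change should be made because it protects the population PK and PK/PD objectives at little cost, and a dose time not collected cannot be reliably recovered later.

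**What to change.** - **Recording.** In protocol sections 3.1.1, 6.3 and 6.4 and the synopsis, replace the morning limit with recording up to the time of the PK draw, for study drug, meals and concomitant medication. The clock time of every visit-day dose before the draw is then on record.
- **Analysis.** In the population PK data analysis plan, use actual time since the most recent dose. Keep the Table 6-1 interval only as a scheduling label. Reassigning samples to the three intervals by most recent dose would not work, because a draw less than 2 h after the second dose fits none of them.
- **Consistency.** Reconcile the dose-timing text in the synopsis and sections 3.1.1, 5.1.3.1 and 5.1.3.2 with the 7–11 h interval and the Table 6-1 column heading. None of this requires a change to dosing.

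The cost is one clause in the protocol and one time field in the diary and eCRF on visit days, with no added visit, procedure or blood draw.
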